7.6.2. Timeframes for Reporting SAEs/SADEs

Prompt notification of the Sponsor regarding SAEs/SADEs is essential so that ethical and regulatory responsibilities and legal obligations can be satisfied. The Investigator must report SAEs/SADEs according to the following time frames:

- **Death or Life-Threatening Event:**

- *Initial notification* must be provided to the Sponsor's Medical Monitor, or designee, **within 24 hours** of the Investigational site learning of the death or life-threatening event (regardless of causality).
- *Complete SAE/SADE information* (i.e., all SAE/SADE pages) must be sent to the Sponsor's Medical Monitor or designee and the Sponsor's clinical operations lead, or designee, **within 24 hours** of receipt of the information by the Investigational site.
- *Follow-up information* must be sent to the Sponsor's Medical Monitor, or designee, **within 24 hours** of receipt of the information by the Investigational site.

- **All other SAEs**

- *Complete SAE information* (i.e., all SAE pages) must be sent to the Sponsor's Medical Monitor, or designee, **within 24 hours** of receipt of the information by the Investigational site.
- *Follow-up information* must be sent to the Sponsor's Medical Monitor, or designee, and the Sponsor's clinical operations lead, or designee, **within 24 hours** of receipt of the information by the Investigational site.

7.6.3. SAE/SADE Information to Report

At a minimum, initial SAE/SADE reports must contain the site name and number, patient ID, patient demographic information, details of study drug administration, the serious adverse event

term, onset date, severity, relationship to study drug, and a brief narrative of the event. If the patient died, the report should include the cause of death and whether or not the death was related to the study drug, as well as any autopsy findings, if available. Please note that **relationship to study drug/causality is very important** and must be included in the initial report as it may impact expedited regulatory reporting requirements for the event. Do not, however, delay reporting of an SAE in order to obtain additional information. Additional information may be reported as a follow-up report as described in Section [7.6.8](#).

Complete SAE/SADE information should be reported in compliance with the Sponsor's Safety Management Plan for this study.

There may be instances when copies of medical records for certain cases are requested. **However, it is not acceptable for the Investigator to send photocopies of the patients' medical records in lieu of completion of the appropriate AE/SAE pages.** If medical records are submitted, all patient personal identifiers must be completely and thoroughly redacted prior to submission.

7.6.4. SAE/SADE Reporting Contact Information

Individual sites should report SAEs to [contact] based on the timeframes given in Section [7.6.2](#).

7.6.5. Clinical Laboratory Abnormalities and Other Abnormal Assessments as TEAEs and SAEs

The Investigator should exercise his or her medical and scientific judgment in deciding whether an abnormal laboratory finding or other abnormal assessment is clinically relevant.

Abnormal laboratory findings (e.g., clinical chemistry, hematology) or other abnormal assessments (e.g., vital signs) that are judged by the Investigator as clinically relevant must be recorded in the medical history or as TEAEs or SAEs if they meet the definition of an adverse event. Clinically relevant abnormal laboratory findings or other abnormal assessments that are detected after the first inhalation of LIQ861, or that are present before administration of LIQ861 but worsen after the first inhalation of LIQ861, should be assessed for AE criteria.

7.6.6. Documenting SAEs/SADEs

A separate set of SAE pages should be used for each SAE. However, if at the time of initial reporting, multiple SAEs are present that are temporally and/or clinically related, they may be reported on the same SAE page.

The Investigator should attempt to establish a diagnosis of the event based on signs, symptoms, and/or other clinical information. In such cases, the diagnosis should be documented as the TEAE and/or SAE term.

7.6.7. Regulatory/Ethics reporting requirement

The Investigator must comply with the applicable local regulatory requirements related to the reporting of SAEs to the Sponsor. Additionally, the Investigator will be responsible for submitting SAE reports to the IRB/EC.

The Sponsor, or designee, will be responsible for submitting SAE reports to applicable regulatory authorities.

7.6.8. Follow-up of TEAEs and SAEs

All TEAEs and SAEs documented at a previous visit/contact that are designated as ongoing will be reviewed at subsequent visits/contacts. TEAEs and SAEs will be followed until resolution, until the condition stabilizes, or until the patient is lost to follow-up. Once resolved, the appropriate TEAE/SAE eCRF page(s) will be updated. If a patient dies during participation in the study or during a recognized follow-up period, a copy of any post-mortem findings, including histopathology, should be obtained, if available, and forwarded to the Sponsor, or designee. New or updated information will be recorded on the originally completed SAE Report Form with all changes signed and dated by the Investigator, or designee.

8. STATISTICS

An integrated statistical and PK analysis plan (SAP) will provide details of planned analyses and summary documents, such as tables, listings and figures. An overview of the planned analyses is provided here. However, final analyses may not be limited to the summaries described herein.

8.1. Determination of Sample Size

Safety Study: Approximately 130 patients will be enrolled in the Main Study to ensure that at least 100 patients are evaluated for safety.

PK Sub-Study: The PK Sub-Study will enroll at least 18 PAH patients to evaluate the comparative bioavailability of treprostinil from LIQ861 to treprostinil from Tyvaso. The number of patients enrolled is sufficient to support such pharmacokinetic analyses.

8.2. Analysis Populations

The analysis populations are defined as follows:

- **Safety Population** will include all patients who receive at least one inhalation of LIQ861 and provide at least one post-Baseline safety assessment.
- **Pharmacokinetic Population (PK Population)** will include all patients in the PK Sub-Study who have not had any adverse events or protocol violations deemed to impact the PK, and have sufficient quantifiable samples collected for estimation of pharmacokinetic parameters from Day 1 of the crossover.

Safety endpoints will be reported for patients in the Safety Population. PK analyses will be performed on patients in the PK population. Inclusion of various populations in specific exploratory analyses will be defined in the SAP.

8.3. Baseline Characteristics and Patient Disposition

Overall Baseline and demographic data will be summarized using descriptive statistics. Patient disposition (e.g., the number of patients enrolled, completed, and discontinued) will be summarized and medical history data will be listed.

8.4. Hypothesis

No formal hypothesis testing is planned.

8.5. Exploratory Analyses

All analyses for the exploratory endpoints described in Section 3.2.4 will be described in the SAP.

8.6. Noncompartmental Pharmacokinetic Analyses (PK sub-study)

Treprostinil concentrations will be summarized, by treatment, using descriptive statistics (including sample size (N), mean, standard deviation (SD), coefficient of variation (CV%), median, minimum, and maximum) for each treatment. Concentrations below the limit of quantification (BLQ) will be treated as zero for the computation of descriptive statistics and for construction of mean concentration-time profiles. Concentrations assigned a value of missing will be omitted from the calculation of descriptive statistics.

For pharmacokinetic analysis, treprostinil concentrations below the limit of quantification (BLQ) will be assigned a value of zero when they precede quantifiable samples in the initial portion of the profile. Following Cmax, BLQ values embedded between two quantifiable data points will be treated as missing when calculating area under the curve. BLQ values occurring at the end of the collection interval (after the last quantifiable concentration) will be treated as missing data. When consecutive BLQ concentrations follow quantifiable concentrations in the terminal portion of the concentration curve, these quantified values will be excluded from the PK analysis by assigning them a value of missing, unless otherwise warranted by the concentration-time profile.

The PK parameters in Table 1 will be estimated by noncompartmental methods from plasma samples. Actual elapsed time from dosing will be used to estimate all individual PK parameters. The final list of PK parameters reported will be described in the SAP.

Table 1. Pharmacokinetic Parameters

Cmax	Maximum observed plasma concentration
Tmax	Time of maximum concentration (h), obtained directly from the observed concentration versus time data.
AUClast	Area under the plasma concentration-time curve from time 0 to time of last measurable plasma concentration
AUCinf	Area under the plasma concentration-time curve from 0-time extrapolated to infinity
AUCext	The percentage of the AUC that is extrapolated beyond the last measurable concentration
λ_z	Apparent plasma terminal-phase elimination rate constant
$t_{1/2}$	Terminal-phase half life
Vz/F	Apparent volume of distribution, terminal phase
CL/F	Apparent systemic clearance
MRT	Mean residence time
Frel	Relative Bioavailability in %

Derived plasma PK descriptive statistics will be tabulated by treatment and reported with summary statistics. Descriptive statistics for PK parameters (Cmax, Tmax, AUClast, AUCinf, λ_z , $t_{1/2}$, Vz/F, CL/F, Frel) will include the arithmetic and geometric mean (for Cmax, AUClast, and AUCinf, only), CV%, SD of the arithmetic mean, median, minimum, maximum, and N.

Relative bioavailability (Frel) will be calculated for all patients that complete both days of the PK sub-study assessments using the following formula:

$$Frel = \frac{AUCinf_{LIQ861}}{AUCinf_{Tyvaso}} \times \frac{Dose_{Tyvaso}}{Dose_{LIQ861}}$$

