	
AUC that is extrapolated beyond the last measurable concentration (AUCext), the terminal phase rate constant (λz), the apparent systemic clearance (CL/F), the apparent volume of distribution in the terminal phase (Vz/F), mean residence time (MRT), and the terminal phase half-life ($t^{1/2}$) will be calculated using non-compartmental analyses.
 
• An assessment of comparative bioavailability of treprostinil will also be made between LIQ861 and Tyvaso based on dose-normalized AUCinf calculations for the two treatments.
STATISTICAL CONSIDERATIONS	
• Individual and mean plots of plasma concentrations versus time after administration of treprostinil will be constructed and displayed for relevant treatment comparisons.• Plasma concentrations will be summarized by treatment using descriptive statistics (sample size, mean, median, coefficient of variation [CV%], standard deviation [SD], minimum, and maximum). Corresponding by-patient data listings will be tabulated.• Derived plasma PK parameters will be summarized by treatment using descriptive statistics (sample size, arithmetic and geometric mean, CV%, SD of the arithmetic mean, median, minimum, and maximum).• The number and percentage of patients who experience at least 1 AE will be presented by severity, relationship to study drug, MedDRA System Organ Class (SOC), preferred term, and dose level of one or both drugs administered. Clinically significant vital signs findings and changes from Baseline values will be tabulated and summarized. Clinical laboratory results will be tabulated.

TABLE OF CONTENTS

PROTOCOL APPROVAL PAGE	2
INVESTIGATOR PROTOCOL AGREEMENT	3
SUMMARY OF AMENDMENT CHANGES.....	4
SYNOPSIS	6
TABLE OF CONTENTS	12
1. INTRODUCTION	17
1.1. Background & Rationale for LIQ861 Development.....	17
1.2. Description of LIQ861	18
1.3. Development Program	19
1.4. Rationale for the Current Study	19
2. STUDY OBJECTIVES	19
3. INVESTIGATIONAL PLAN	19
3.1. Overall Study Design and Plan	19
3.2. Endpoints	21
3.2.1. Primary Endpoint	21
3.2.2. Safety Endpoints	21
3.2.3. Pharmacokinetic Endpoints.....	22
3.2.4. Exploratory Endpoints	22
4. SELECTION OF STUDY POPULATION	22
4.1. Inclusion Criteria.....	22
4.2. Exclusion Criteria.....	23
4.3. Removal of Patients from Therapy/Premature Discontinuation	24
5. TREATMENTS	25
5.1. Treatments Administered	25
5.2. Identity of Investigational Product(s).....	25
5.2.1. LIQ861	25
5.2.2. Labeling.....	26

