3.2.3. Pharmacokinetic Endpoints

For patients in the PK sub-study only:

- Individual pharmacokinetic parameters for treprostinil will be summarized by treatment using descriptive statistics. Pharmacokinetic parameters such as the maximum observed plasma concentration (Cmax), time to Cmax (Tmax), the area under the plasma concentration versus time curve from time 0 (predose) to time infinity (AUCinf), AUC from time 0 to time of last measurable plasma concentration (AUClast), the percentage of AUC that is extrapolated beyond the last measurable concentration (AUCext), the terminal phase rate constant (λ_z), the apparent systemic clearance (CL/F), the apparent volume of distribution in the terminal phase (Vz/F), mean residence time (MRT), and the terminal phase half-life ($t_{1/2}$) will be calculated using non-compartmental analyses.
- An assessment of comparative bioavailability of treprostinil will also be made between LIQ861 and Tyvaso based on dose-normalized AUCinf calculations for the two treatments.

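### Protocol 8.6 reverses the order in its terminal BLQ rule: followed literally, it discards valid concentrations and costs Frel precision, though not its centre

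*Protocol*

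**What the plan says.** Protocol 8.6 handles post-Cmax BLQ values in three steps.

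- A BLQ lying between two quantifiable points is treated as missing when the AUC is calculated.
- For the tail, "BLQ values occurring at the end of the collection interval (after the last quantifiable concentration) will be treated as missing data".
- The last step has this trigger: "When consecutive BLQ concentrations follow quantifiable concentrations in the terminal portion of the concentration curve". The action that follows falls on the measured concentrations and not on the BLQs: "these quantified values will be excluded from the PK analysis by assigning them a value of missing, unless otherwise warranted by the concentration-time profile".

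Table 1 in the same section defines AUClast as "Area under the plasma concentration-time curve from time 0 to time of last measurable plasma concentration".

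The comparison of formulations is "based on dose-normalized AUCinf calculations for the two treatments" (Protocol 3.2.3). Section 8.6 turns this into a per-patient Frel, the AUCinf ratio multiplied by the inverse dose ratio. Its descriptive statistics "will include the arithmetic and geometric mean (for Cmax, AUClast, and AUCinf, only"), plus CV%, SD, median, range and N. Frel therefore gets an arithmetic mean and a median but no geometric mean. The Synopsis lists the geometric mean for derived parameters without that limit. Neither list includes a confidence interval.

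Protocol 8 calls its content an overview and adds that "final analyses may not be limited to the summaries described herein". SAP 4.3 refers to the protocol and a separate PK SAP, which is not among the documents, and says the PK data have already been reported.

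**The concern.** A treprostinil profile that decays below the assay limit before 4 hours ends in a run of BLQ values. That is ordinary behaviour and gives no reason to doubt the concentrations before the run. The literal rule nevertheless makes deleting them the default.

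The usual purpose of such a rule is the opposite case: an isolated quantifiable value that reappears after two or more BLQs. As written, that case has no exclusion rule at all, and the embedded-BLQ sentence would keep the reappearing value. The sentence reads like a reversal of order.

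If it were followed, AUClast would stop short of its own definition. The terminal slope would be fitted to earlier points, and some patients could lose AUCinf altogether. AUCinf feeds Frel, which serves the secondary objective in a sub-study planned for at least 18 patients.

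**Working it through.** **1. The sentences side by side.** Suppose the 3 h and 4 h samples are BLQ. The preceding sentence drops those two, so the profile ends at 2 h and AUClast runs to 2 h. The literal rule then also drops quantified values. The end of the profile moves to 1.5 h if one is dropped, 1 h if two, and 0.75 h if three (sampling times from Protocol 6.4). The text does not say how many.

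**2. Inputs for the size.** The plan states no figure to reproduce.

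- From the protocol: the 13 sampling times, Tmax of 10-20 min for LIQ861 (Protocol 1.3), and n of at least 18.
- Assumed, because the documents give none: half-life 0.4, 0.5, 0.6 or 0.75 h; assay limit 2, 5 or 10% of Cmax; independent log-normal assay noise with CV 15%.
- Two profile shapes: one-phase with Tmax 15 min; and two-phase with 70% fast decay (half-life 0.25 h), 30% slow decay at the grid half-life, and input rate 12/h.
- Method, also assumed: linear trapezoid; terminal slope λz from the last three retained points; AUCinf = AUClast + Clast/λz. AUCinf is non-estimable with fewer than three post-Cmax points or a slope that is not negative.

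Each profile ending in two or more BLQs was analysed with every quantifiable point, then with the last one, two or three removed. For Frel, both days had the same underlying shape and the rule was applied to each day.

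**3. Results.**

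| Points deleted | AUClast, noise-free | Median AUCinf change (one-phase / two-phase) | SD of log Frel | Frel non-estimable |
|---|---|---|---|---|
| 0 | reference | reference | about 0.08 | reference |
| 1 | -3 to -16% | about 0 / -2% | about 0.13 | about 1% |
| 2 | -13 to -33% | about +1 / -4% | about 0.3 | about 6-8% |
| 3 | -23 to -50% | about +5 / -5% | about 0.56 | about 23-28% |

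Median Frel stays at 1.00 throughout. The last two columns cover all simulated patients, including those whose profiles never triggered the rule. In 18 patients, the losses amount to 18 × 0.01 = 0.2, 18 × 0.06 to 0.08 = 1.1-1.4, and 18 × 0.23 to 0.28 = 4.1-5.0 patients.

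**4. Adding real day-to-day variation.** The SDs above contain assay noise only. Suppose true variation in the ratio has CV 30%, so its log variance is ln(1.09) = 0.0862, independent of the noise. The total SD is then √(0.0862 + 0.08²) = 0.30 with no deletion. It becomes √(0.0862 + 0.13²) = 0.32, √(0.0862 + 0.3²) = 0.42 and √(0.0862 + 0.56²) = 0.63 with one, two and three deletions. One deletion then costs little; two or three cost a good deal.

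**5. The summary for Frel.** If ratios are log-normal, arithmetic mean / typical ratio = √(1 + CV²). The 90% interval factor for a paired geometric mean ratio is exp(t × √ln(1 + CV²) / √n), with n = 18 and t(0.95, 17) = 1.740.

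| Assumed ratio CV | Arithmetic mean above typical ratio | 90% interval: ratio ×/÷ |
|---|---|---|
| 20% | 2% | 1.08 |
| 30% | 4% | 1.13 |
| 40% | 8% | 1.17 |
| 50% | 12% | 1.21 |

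**The case against.** The strongest reply is that this is a drafting slip with no shown consequence. The exception clause lets an analyst keep the values. Section 8 is an overview, the detail belongs in a PK SAP that cannot be seen here, and the PK results are already reported. An experienced pharmacokineticist may well have applied the sensible rule. All of that stands, and it is why the first step is a check. It does not clear the text. The clause leaves deletion as the default, with no criterion for departing from it, and SAP 4.3 still names the protocol as a source for the PK endpoints.

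A reader might infer that the two tail sentences cannot both be followed. They can: BLQs and quantified values can both be set to missing. The clash is one of effect, because the second removes the point that the first leaves as the end of the profile.

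A reader might also infer that the bioavailability ratio is biased. The calculation does not show that. Frel uses AUCinf, so the AUClast losses do not pass straight into it. Median AUCinf moves by only about 5% either way, and with similar shapes on both days median Frel is unshifted.

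On the summary statistics, the study is descriptive (Protocol 8.4), so the absence of an interval breaks no test. The planned median already estimates a typical ratio. The planned SD and N give an arithmetic half-width of t × CV/√18 = 8, 12, 16 and 21% at the same four CVs, so approximate precision can be derived. What remains is a convenience: one ratio-scale estimate with its interval.

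**Conclusion.** The rule is wrong as written. It removes valid concentrations that the preceding sentence and Table 1 depend on, and its exception repairs this only case by case.

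If it was applied, AUClast would be shortened in every affected profile, by 3-50% depending on how many points are deleted. For Frel the harm is lost precision and lost patients: small with one deletion, substantial with two or three. These sizes rest on assumed half-lives, assay limits, noise and NCA settings. How often the rule would fire depends mainly on the assay limit, which the documents do not give, so no frequency is claimed. The unshifted median rests on similar profile shapes for Tyvaso and LIQ861.

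The documents do not show that the reported analysis used the literal rule, and nothing here says the reported ratio is wrong. The geometric mean ratio is a secondary, optional improvement.

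**What to change.** 1. Reword the sentence to: *quantifiable concentrations that occur after two or more consecutive BLQ values in the terminal portion are set to missing*, keeping the existing exception clause.
2. State that this takes precedence over the embedded-BLQ rule, which then covers single embedded BLQs. Otherwise a sequence of quantifiable, BLQ, BLQ, quantifiable falls under both rules with opposite results.
3. Confirm which rule the PK SAP and the reported analysis used. Re-run as an addendum only if the literal rule was applied.
4. As a secondary step, report the paired geometric mean ratio (LIQ861/Tyvaso) of dose-normalised AUCinf with a 90% interval beside the planned summaries, labelled as estimation, and align the Synopsis with Section 8.6 on the geometric mean.

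The cost is a short wording change, one check and one paired analysis of existing data. Sample size and data collection do not change. The downside of step 4 is one more result, which could be misread as an equivalence test unless clearly labelled.

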8.7. Safety Analyses

Extent of Exposure, Adverse Events, Adverse Device Effects, Clinical Laboratory Assessments, and Vital Signs will be summarized with descriptive statistics.

8.7.1. Prior and Concomitant Medications

Medications taken after the patient receives study drug through Study Termination or Follow-up to Early Termination will be listed by treatment, dose level, and patient.

9. RESPONSIBILITIES

9.1. Investigator Responsibilities

9.1.1. Good Clinical Practice

The Investigator will ensure that this study is conducted in full compliance with the principles of the “Declaration of Helsinki”, ICH guidelines, or with the laws and regulations of the country in which the research is conducted, whichever affords the greater protection to the study patient. For studies conducted under a United States IND, such as this study, the Investigator will ensure that the basic principles of “Good Clinical Practice,” as outlined in 21 CFR 312, subpart D, “Responsibilities of Sponsors and Investigators,” 21 CFR, part 50 and 21 CFR, part 56 are adhered to. The PK sub-study study is also subject to and will be conducted in compliance with 21 CFR, part 320, “Retention of Bioavailability and Bioequivalence Testing Samples.”

